8.0 POWER CALCULATION AND DATA ANALYSIS PLAN

Specific Aim 1: Sample size justification: Based on previously collected data by this study team, we assume that the osteoporotic patients will have an average (SD) BMD prior to surgery of 1.15 g/cm² (0.2). We hypothesize that on average there will be minimal (< 0.02 g/cm²) bone loss at the 15 month follow-up. With a SD of 0.2, if we have follow-up data on at least 21 osteoporotic patients, we will have 86% power with a two-sided one-sample t-test to conclude that ABL effectively reduces bone loss less than 0.16g/cm². To account for up to 26.5% attrition previously reported in the pivotal ABL study,⁴³ we will enroll and treat 29 osteoporotic patients under going TKA.

Specific Aim 2: Sample size justification: If we assume that there will be a medium to large (Cohen's D = 0.65) effect in the paired differences of BMD from baseline to 15 months post TKA in an osteopenic population, then we will need to recruit 21 patients to have 80% power to detect this effect size. To account for up to 26.5% attrition we will enroll and follow 29 osteopenic patients under going TKA.

Baseline demographic and characteristic variables will be summarized with mean (SD), median (IQR), or N (%) based on the statistical distribution of the variable. The primary comparison will be on the change in distal femoral BMD at 25% ROI of the surgical leg from 3 months pre-TKA to 15 months post-TKA. We will test for a significant difference in the osteoporotic population versus a null hypothesis of -0.16g/cm² with a two-sided one-sample t-test. Similarly, we will test for a significant change in BMD in the osteopenic population versus a null hypothesis of 0g/cm² with a one-sample t-test. Exploratory analyses will compare the change in BMD over time between osteoporotic patients treated with ALB and untreated osteopenic patients with repeated measures ANOVA while controlling for age, sex, and BMI as covariates and treating patient as a random effect. Changes over time in secondary variables

will be estimated by paired differences and tested for significant changes from baseline with paired t-tests. All tests will be conducted at a 5% significance level.

If a subject drops out or is lost to follow-up prior to data collection at time of surgery, they will be completely removed from the study and a new participant will take their place. If a subject drops out or is loss to follow-up after surgery, they will remain in the study and we will implement various data imputation methods like last observation carried forward (LOCF) and linear prediction imputation.

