3.0 PRELIMINARY DATA

3.1 Meta-analysis of BMD loss after TKA (See Prince, et. al.)³⁹

This meta-analysis of 14 studies that quantified distal femur BMD change after primary TKA. In the distal femoral supracondylar region, mean BMD losses of 0.09 [0.05,0.13], 0.14 [0.08,0.20], 0.16 [0.10,0.23], and 0.16 [0.12,0.20] g/cm² were reported 3, 6, 12, and 24 months respectively following TKA. This corresponds to a 9.3%, 13.2%, 15.8%, and 15.4% BMD loss at these time points. In summary, there is a rapid and significant ~15% decrease in BMD in the first 6 months after TKA that is sustained to 24 months. Better understanding regarding how pre-/perioperative bone health optimization may affect BMD loss and the subsequent periprosthetic fracture risk of is essential.

3.2 Distal femoral BMD and cortical thickness after TKA compared to the contralateral (non-operated) side (See Thomas et. al, and Blaty, et. al.^{22, 23})

We initially performed measurements in 1 cm ROI increments to define BMD change throughout the femur (Thomas, et. al.). Based upon that data, we developed and evaluated a standardized technique to measure BMD and cortical thickness utilizing existing atypical femur fracture DXA software. We then compared distal femoral BMD and cortical thickness on the TKA side to the contralateral non-operative leg (Blaty, et. al.).²³ Thirty adults (15 M/15 F) age 59-80 years with well-functioning unilateral, primary TKA 2-5 years after surgery had femoral DXA scans performed. BMD and cortical thickness were measured at ROIs located at 15%, 25%, and 60% of the femur length measured from the distal notch. Femur BMD and cortical thickness were compared between limbs (TKA vs. non-operated side) by paired t-test.

BMD was 9.7%, 9.6%, and 3.2% lower ($p < 0.0001$) in the operated femur at the 15%, 25%, and 60% ROI respectively. Evaluation of this cohort by BMD status (normal, osteopenia, osteoporosis) finds distal femur BMD at the 25% ROI to be 12% lower in those with osteopenia and 10.3% lower in those with osteoporosis. Cortical width was lower by 22% ($p < 0.05$) at the 25% ROI on the TKA side but not at the 15 or 60% ROI, likely due to current software limitations. Importantly, at these distal femur ROIs, BMD reproducibility was excellent, despite

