4.2 Participant recruitment and study design

Study participants will be recruited from the UW Total Joint Program at the American Center. Patients expressing interest in study participation at the time of TKA scheduling will subsequently be contacted by a University of Wisconsin Osteoporosis Clinical Research Program (OCRP) study coordinator. Those expressing study interest will be scheduled at the OCRP where, following informed consent, medical history, collection of FRAX risk factors and a screening DXA of the lumbar spine, bilateral femurs/hips and VFA will be performed.

The overall study design is noted in Figure 1. Briefly, study eligibility will be determined by DXA. Those with osteoporosis who elect ABL will make up the treatment group ($n = 29$). An equal number ($n = 29$) will be recruited into the untreated group, i.e., those with osteopenia and no prior fragility fracture.

At screening, all participants will have a physical examination and blood collected for a metabolic panel, 25(OH)D and parathyroid hormone (PTH) measurement with additional sample to bank for potential future testing related to bone metabolism. Additionally, calcium and PRO questionnaires will be collected consisting of the KOOS JR, VR-12, and Forgotten Joint Survey. Subjects will be advised on how to achieve a daily calcium intake of 1,000-1,200 mg through food plus supplements, if needed, and up to 4000 IU of vitamin D₃ daily (as noted below; section 5.1). Subsequently, for those meeting all inclusion/exclusion criteria, ABL will be initiated in the treatment group approximately 3 months (depending on the surgery schedule) prior to their TKA and serum calcium will be assessed after one month of dosing. Subsequently, all subjects will have lumbar spine and bilateral femur DXA repeated within two weeks prior to TKA (± 7 days from the month -0.25 study visit) and again 6 and 15 months post TKA. At these same visits, PRO questionnaires will be administered and blood will be collected for serum banking.

Figure 1: Study Design Schematic

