5.1 Screening

Interested subjects will provide written informed consent and self-reported medical history to confirm study eligibility. Those meeting eligibility criteria will have DXA scans (lumbar spine, bilateral femur/hip, forearm and VFA) performed. Those with normal bone density based on a female normative database (i.e., T-scores ≥ 1.0) at the femoral neck, total proximal femur and lumbar spine (with vertebral exclusion per ISCD recommendations), will be excluded from further participation. Remaining potential subjects will receive PA and lateral knee DXA, body composition measurement by DXA and BIS, a physical exam with vitals (blood pressure, pulse, height and weight), complete a dietary calcium assessment and PRO questionnaires to include KOOS JR, VR-12 and Forgotten Joint Survey. Additionally, they will have blood collected to measure a comprehensive metabolic panel, PTH and total 25(OH)D. Samples will

also be collected for potential future testing related to bone metabolism related to this protocol. Those with abnormal calcium, creatinine, albumin, PTH or 25(OH)D < 10 ng/mL will be excluded from the study. DXA results performed within the prior 6 months on the research scanner are acceptable for the screening visit. Laboratory values and PRO questionnaires collected as part of a UWHealth evaluation in the 6 months prior to the screening visit can be utilized as screening data. Additionally, physical exam may be delayed to the initiation visit for the treatment group or pre-surgery visit for osteopenic group.

Subjects meeting the entry criteria based on osteoporosis diagnosis (T-score \leq -2.5 or -1.1 with prevalent vertebral fracture or recent low trauma clinical fracture) will discuss ABL treatment and those electing to participate will receive training on how to administer the medicine using the Radius ABL Instructions for Use (IFU) manual. Subjects declining treatment will be excluded from the study. Subjects in the osteopenia group will have a lowest BMD T-score of -1.1 to -2.4 at the lumbar spine, femoral neck or total proximal femur and a negative fragility fracture history.

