5.4 Pre-TKA Study Visit

All subjects will have TKA surgery approximately 3 months after their screening DXA visit, depending on the surgery schedule. The osteopenic group must have screening data at least 4 weeks prior to but not more than 6 months before this visit. The osteoporotic group must have received at least 8 weeks of ABL prior to this visit. Such variability is acceptable as this reflects clinical care and the primary comparison is BMD change from immediately prior to surgery to 15 months after TKA. As the usual wait time for surgery scheduling in our facility is ~2 months, this should not present a major impediment to study recruitment. The week prior to their scheduled TKA surgery all subjects will return to the OCRP and have repeat lumbar spine, bilateral femur/hip (including distal femur), forearm, PA & bilateral knee and total body DXA measurement, BIS, blood collection and adverse event assessment. Calcium and vitamin D₃ will be dispensed as appropriate. Additionally, subjects will be questioned regarding adverse events, falls and fractures; a physical exam or VFA may be performed if indicated per an investigator. If surgery is delayed for any reason, the study physician will determine if study continuation is appropriate and adjust the study visit timeline as necessary, this may include repeating laboratory tests and/or DXA exams.

5.5 6-month

All subjects will return to the OCRP for DXA (lumbar spine, bilateral femur/hip (including distal femur), forearm, total body, PA & lateral knee), BIS measurement and blood collection. Subjects will be questioned regarding adverse events, falls and fractures and PRO questionnaires will be completed; a physical exam or VFA may be performed if indicated per an investigator. Calcium and vitamin D will be dispensed as needed.

5.6. 15-month

All subjects will return to the OCRP for DXA (lumbar spine, bilateral femur/hip (including distal femur), forearm, PA & lateral knee and total body), BIS measurement and blood collection. Subjects will be questioned regarding adverse events, falls and fractures and PRO questionnaires will be completed; a physical exam or VFA may be performed if indicated per an investigator.

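### Sections 8.0 and 5.4 give the primary BMD comparison two different baselines, and only the pre-surgery one shares the time origin of the -0.16 g/cm² benchmark

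*Combined protocol and SAP*

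**What the plan says.** Two sections of the combined protocol and SAP define the primary comparison.

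- Section 8.0 (analysis plan): "change in distal femoral BMD at 25% ROI of the surgical leg from 3 months pre-TKA to 15 months post-TKA". For the osteoporotic group this change is tested "versus a null hypothesis of -0.16g/cm² with a two-sided one-sample t-test".
- Section 5.4 (pre-TKA visit): "the primary comparison is BMD change from immediately prior to surgery to 15 months after TKA". The sentence is there to justify accepting variable timing before surgery.

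Scans exist for both definitions. Table 1 schedules DXA at screening (Month -3.5) and at Month -0.25, and section 4.2 states that "all subjects will have lumbar spine and bilateral femur DXA repeated within two weeks prior to TKA".

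In the treated group the interval between these scans contains treatment. Section 4.2 says "ABL will be initiated in the treatment group approximately 3 months (depending on the surgery schedule) prior to their TKA", and section 5.4 adds: "The osteoporotic group must have received at least 8 weeks of ABL prior to this visit".

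The benchmark comes from the meta-analysis in section 3.1, whose mean losses "were reported 3, 6, 12, and 24 months respectively following TKA". The 0.16 g/cm² figure is the 12- and 24-month value.

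Sections 2.0 and 2.1 do not settle the matter. They refer to 15 months after TKA or to change from baseline without identifying the baseline scan.

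**The concern.** The primary endpoint is defined twice and no rule of precedence is given. Because both scans will be in the database, the primary result can be computed in either way, and the choice could be made after the data are seen.

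The two versions measure different things in the treated group. The section 5.4 version measures change across surgery and the following 15 months. The section 8.0 version adds the pre-operative treatment period. The null value of -0.16 g/cm² has no such period, since its follow-up is counted from TKA. If BMD at the 25% ROI rises on ABL before surgery, the section 8.0 version counts that rise as protection from post-surgical loss. Aim 1 has no concurrent control arm in which the effect could cancel.

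The osteopenic group is affected differently. It has no ABL gain, but section 5.4 allows its screening data to precede the pre-surgery visit by 4 weeks to 6 months. Aims 2 and 3 therefore also need one stated baseline.

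**Working it through.** **Inputs from the plan (section 8.0):** mean pre-surgery BMD 1.15 g/cm²; SD 0.2 g/cm²; expected loss under 0.02 g/cm², taken as 0.02; null loss 0.16 g/cm²; n = 21 evaluable; two-sided 5% one-sample t-test; attrition 26.5%; 29 enrolled.

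**Assumption:** a pre-operative gain g of 1%, 2% or 3% of 1.15, that is 0.0115, 0.0230 or 0.0345 g/cm². The documents give no figure for g.

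**1. The plan's own figure.** The difference to detect is 0.16 − 0.02 = 0.14. The noncentrality is (0.14/0.2) × √21 = 3.21, and the critical t on 20 df is 2.086. Power from the noncentral t is 86.2%, which agrees with the stated 86%. Enrolment is 21/(1 − 0.265) = 28.6, rounded up to 29. Both reproduce.

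**2. Effect of the section 8.0 baseline.** Suppose ABL leaves post-surgical loss at 0.16 but raises BMD by g before surgery. The change from the earlier scan then has mean −0.16 + g, so it lies g above the null. The noncentrality is (g/0.2) × √21, and the chance of declaring benefit is the upper-tail rejection probability.

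| g (share of 1.15) | g, g/cm² | g/0.16 | noncentrality | chance of declaring benefit |
|---|---|---|---|---|
| 0% | 0 | 0% | 0 | 2.5% |
| 1% | 0.0115 | 7% | 0.26 | 4.4% |
| 2% | 0.0230 | 14% | 0.53 | 7.2% |
| 3% | 0.0345 | 22% | 0.79 | 11.4% |

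A pre-operative fall in BMD would move the result in the opposite direction.

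**3. Effect on power of moving to the pre-surgery baseline.** Section 8.0 does not say which scan the 0.02 loss is measured from.

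- If it is measured from the pre-surgery scan, power stays at 86.2%.
- If it is a net loss from 3 months before TKA, the loss from the pre-surgery scan is 0.02 + g and the difference to detect falls to 0.14 − g:

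| g | difference, g/cm² | power at n = 21 | evaluable n for 86% |
|---|---|---|---|
| 0% | 0.1400 | 86.2% | 21 |
| 1% | 0.1285 | 80.0% | 25 |
| 2% | 0.1170 | 72.3% | 29 |
| 3% | 0.1055 | 63.3% | 36 |

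**The case against.** The strongest reply is that a pre-treatment baseline is a legitimate choice. The hypothesis in section 2.0 concerns ABL given both before and after TKA, so pre-operative dosing is part of the strategy under test. The Month -0.25 scan follows at least 8 weeks of ABL and leaves that part of the effect out. If untreated BMD is roughly stable in the months before surgery (the documents are silent), -0.16 g/cm² is also a reasonable null from the earlier scan. The 4–11% would then not be false positives, because ABL really would have raised BMD. This stands. It answers a reader who might infer that the section 8.0 baseline is simply biased towards success. The figures are errors only if the target is post-surgical loss alone, and only if BMD at this ROI rises before surgery.

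Two further limits also stand. Section 3.1 says that follow-up is counted from TKA but not which baseline scan the pooled studies used. Section 8.0 names a time, 3 months before TKA, rather than a visit; that it means the screening scan is a reasonable inference from Table 1.

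A reader might also stack the allowance in section 5.1, "DXA results performed within the prior 6 months on the research scanner are acceptable for the screening visit", on the 12 weeks in section 5.2 and conclude that the baseline could lie about 9 months before treatment. That is a worst case, limited by the section 5.2 rule that scans be repeated if ABL starts more than 12 weeks after screening. The extra time is untreated, so it adds variability in timing but no ABL gain.

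Finally, the section 5.4 wording is a scheduling rationale, and it could be said that the analysis section governs. No provision says so, and the rationale for flexible timing fails under the section 8.0 definition.

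**Conclusion.** The contradiction is established by the text alone. The same primary comparison has two start points that differ, in the treated group, by at least 8 weeks of ABL, and the documents do not reconcile them. The difference in time origin between the section 8.0 change and the -0.16 g/cm² benchmark also follows from the text.

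Its numerical consequence is conditional. With an assumed pre-operative gain of 1–3%, the plan's SD of 0.2 and n = 21, the chance of declaring benefit when post-surgical loss is unaffected rises from 2.5% to about 4–11%. The documents do not support a firmer claim of bias, because they give neither the size nor the direction of the pre-operative change.

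Nor should a reader infer that the sample-size arithmetic is wrong: 86% power and 29 enrolled both reproduce. The fault is in the endpoint definition, and it must be corrected before the primary analysis.

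**What to change.** - Name one primary baseline, by visit and scan, in identical terms in sections 5.4 and 8.0, before any outcome data are analysed, and apply it to Aims 1 to 3.
- The Month -0.25 scan is the natural choice if the target is loss after surgery. It agrees with section 5.4 and with the benchmark's time origin. It should also be available for every analysed patient, because section 8.0 removes and replaces those lost before data collection at surgery.
- Report two labelled secondary or sensitivity estimates: the change from the pre-treatment scan to month 15, which describes the whole pre- plus post-operative strategy, and the change from screening to the pre-surgery scan. State which scan is the pre-treatment one where DXA is repeated at initiation.
- If the sponsor prefers the pre-treatment baseline as primary, amend section 5.4 and justify using -0.16 g/cm² as the null over the longer interval.
- State which baseline the expected 0.02 g/cm² loss and the SD of 0.2 refer to.

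**Cost.** No new visits or scans are needed. If the 0.02 loss already refers to the pre-surgery scan, the change is wording only. If it was a net loss from 3 months before TKA, the 86% power must be restated: about 80%, 72% or 63% at n = 21 for assumed gains of 1%, 2% or 3%, with 25, 29 or 36 evaluable patients needed to regain 86%.

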2.0 STUDY OBJECTIVE

Based on the above, it is clear that bone anabolic agents are of interest in orthopedic surgical patients. A recent review on non-classical use of anabolic agents concluded *“Based on a large array of literature, patients with osteoporosis require bone interventions.... Would benefit from an anabolic agent over the use of anti-resorptive agent”* and *“additional studies are needed to substantiate the role of other anabolic agents such as abaloparatide...”*³⁸ **To this end, we hypothesize that treating osteoporotic patients with ABL prior to and after TKA will significantly reduce the amount of bone loss, as measured by BMD at the 25% distal femur ROI, 15 months post TKA.** To assess the effect of ABL, we will compare the bone loss seen in this study to the 0.16 g/cm² average BMD lost in untreated osteoporotic patients at 12 and 24 months following TKA reported in Prince et.al.³⁹

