2.1 Primary Study Endpoints

Specific Aim 1: To estimate the amount of distal femur bone loss in ABL treated osteoporotic patients 15 months post TKA and to compare the bone loss to the bone loss seen in untreated osteoporotic patients 12 months following TKA as reported by the meta-analysis of Prince et.al.³⁹ The limitation of this design is the comparison to a historic control rather than a control arm in this study. The reason this design was chosen is because it would be unethical to not offer treatment to newly diagnosed osteoporotic patients. Therefore, randomization to a control arm is not possible. Furthermore, based on our recent clinical experience we believe the rate of patient choice to refuse treatment will be quite low making recruitment of a non-randomized osteoporotic control arm futile. This reflects a dramatic change in osteoporosis care within orthopedic surgical practice at UW within the past year. Lastly, it is well documented that bone loss will occur in this patient population following TKA as seen in the multiple studies summarized in the Prince article.

Specific Aim 2: To estimate the amount of distal femur bone loss in untreated osteopenic patients 15 months post TKA.

The hypothesis for this aim is that TKA will significantly reduce BMD from baseline to 15 months post surgery in osteopenic patients. To assess this we will conduct a single arm pre-post observational study.

This design was chosen because data in the literature is sparse for BMD levels pre and post TKA in an osteopenic population. Collection of these data could demonstrate significant reduction in BMD following TKA which would lead to the justification of a future prospective study comparing a bone loss mitigating treatment to no treatment (current standard of care) in osteopenic TKA patients.

Specific Aim 3: To compare the amount of bone loss in ABL treated osteoporotic patients to untreated osteopenic patients 15 months following TKA.

The hypothesis for this aim is that the percent decrease from baseline in BMD at 15 months post TKA will be greater in the untreated osteopenic group compared to the treated osteoporotic group.

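### The Aim 1 test takes the historical loss of 0.16 g/cm² as known: for the comparison with untreated patients, two-sided error is about 11% (12-month interval) or 7% (24-month interval), not 5%

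*Combined protocol and SAP*

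**What the plan says.** Section 8.0 sets the primary Aim 1 test: "We will test for a significant difference in the osteoporotic population versus a null hypothesis of -0.16g/cm² with a two-sided one-sample t-test". The power statement in the same section assumes an SD of 0.2 g/cm², at least 21 osteoporotic patients with follow-up and a 5% two-sided level. On the treated group it says: "We hypothesize that on average there will be minimal (< 0.02 g/cm²) bone loss at the 15 month follow-up". It arrives at 86% power and, after 26.5% attrition, 29 patients enrolled.

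The benchmark comes from the meta-analysis summarised in section 3.1, which reports "mean BMD losses of 0.09 [0.05,0.13], 0.14 [0.08,0.20], 0.16 [0.10,0.23], and 0.16 [0.12,0.20] g/cm²" at 3, 6, 12 and 24 months. The brackets carry no confidence level.

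The sections differ on the comparator's time point. Section 2.0 refers to the "0.16 g/cm² average BMD lost in untreated osteoporotic patients at 12 and 24 months following TKA". Aim 1 in section 2.1 names only the "bone loss seen in untreated osteoporotic patients 12 months following TKA as reported by the meta-analysis". Follow-up in this trial is at 15 months, between the two.

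Section 2.1 is open about the design: "The limitation of this design is the comparison to a historic control rather than a control arm in this study". It does not mention the sampling error of the historical figure, and no other section does.

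**The concern.** The stated aim is a contrast between two means: loss on ABL and loss without treatment. Both are estimated. The one-sample t-test uses the standard error of the first and sets that of the second to zero. That is harmless when the benchmark is known far more precisely than the trial mean. Here the two standard errors are of similar size.

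At stake are the p-value and confidence interval for the main claim, which would be too optimistic as statements about treated versus untreated patients. The study has no concurrent untreated osteoporotic group against which an over-confident result could be checked.

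**Working it through.** **Inputs.** From section 8.0: null value −0.16 g/cm², SD 0.2, n = 21, expected loss 0.02, two-sided α = 0.05. From section 3.1: 0.16 [0.10, 0.23] at 12 months and 0.16 [0.12, 0.20] at 24 months. Assumption: the brackets are 95% confidence intervals.

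**1. The plan's own figure.** Difference = 0.16 − 0.02 = 0.14. Trial SE = 0.2/√21 = 0.0436. Exact noncentral-t power with 20 df is 86.2%, which reproduces the stated 86%. Attrition: 21/(1 − 0.265) = 28.6, so 29.

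**2. Standard error of the benchmark.** SE_hist = interval width/(2 × 1.96).
- 12 months: (0.23 − 0.10)/3.92 = 0.0332
- 24 months: (0.20 − 0.12)/3.92 = 0.0204

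**3. Standard error of the contrast.** √(s²/n + SE_hist²).
- 12 months: √(0.0436² + 0.0332²) = 0.0548
- 24 months: √(0.0436² + 0.0204²) = 0.0482

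**4. Error of the planned test for the Aim 1 question.** Suppose ABL patients lose exactly what untreated patients lose. The planned test still divides by 0.0436, although the contrast varies with SE 0.0548 (or 0.0482). As a normal approximation, the effective critical value is 1.96 × 0.0436/0.0548 = 1.56, an error of about 12%; with the 24-month interval it is 1.96 × 0.0436/0.0482 = 1.77, about 8%. Simulating the t-test itself (1,000,000 runs, benchmark drawn with its SE) gives the figures below.

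**5. A test carrying both errors.** T = (mean change + 0.16)/√(s²/n + SE_hist²), with Satterthwaite df = (s²/n + SE_hist²)²/[(s²/n)²/(n − 1)], which is about 50 (12-month) or 30 (24-month) at s = 0.2. In simulation it holds 5%.

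Results at SD 0.2, n = 21, true loss on ABL 0.14 below the untreated mean for power:

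| | 12-month interval | 24-month interval |
|---|---|---|
| Planned test, two-sided error | 11.2% | 7.3% |
| of which favourable (nominal 2.5%) | 5.6% | 3.7% |
| Planned test, power averaged over benchmark error | 81% | 84% |
| Test carrying both errors, power | 70.7% | 80.3% |

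**6. Sensitivity.** If all 29 enrolled patients are evaluable, the planned test's error is 13.8% (12-month) or 8.4% (24-month): a more precise trial mean makes the neglected term matter more. The SD also matters. Section 8.0 gives 0.2 for BMD before surgery and reuses it for the change; the SD of change is not in the documents. With the 12-month interval and n = 21:

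| SD of change | Planned test, error | Test carrying both errors, power |
|---|---|---|
| 0.20 (plan) | 11% | 71% |
| 0.13 (assumed) | 19% | 89% |
| 0.10 (assumed) | about 26% | 94% |

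Error and corrected power rise together, so figures from different rows must not be combined.

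**The case against.** The best defence is that comparing a single arm with a fixed benchmark is common and transparent, and that the plan openly calls the historical control its limitation. Against its literal null, a mean change of −0.16, the t-test has exactly 5% error and 86% power. All of that stands. The inflation concerns the wider inference about untreated patients, and half of it lies in the unfavourable direction. But that wider inference is what Aim 1 states, and the acknowledged limitation concerns the design and does not reach the standard error.

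A reader might go further in four ways that the documents do not support:
- **That the 86% is miscalculated, or that the planned test really has 71% power.** The 86% reproduces. The 71% belongs to a different test; the planned test, averaged over benchmark error, rejects about 81% of the time.
- **That error could be 26% while power is only 71%.** The 26% needs an SD of change near 0.10, which the documents do not give, and there the corrected power is about 94%. A similar figure, 25.8%, arises at SD 0.2 only if the true untreated loss sits exactly at the lower limit of 0.10.
- **That section 3.1 states a 95% interval.** It prints brackets without a level. 95% is a reasonable reading, but it is an assumption behind every figure here.
- **That only the 12-month interval counts.** Aim 1 names 12 months, but section 2.0 names 24 months as well, and that interval gives the milder result.

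It is also fair to say that adding SE_hist gives limited protection. It covers the sampling error of a pooled mean. It does not cover the step from the supracondylar region in 14 studies of primary TKA to the 25% ROI in osteoporotic patients.

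**Conclusion.** The concern holds for the comparison that Aim 1 makes, not for the literal test against a constant. On the plan's own SD of 0.2 and 21 completers, and reading the brackets as 95% confidence intervals, the two-sided error is about 11% (12-month interval) or 7% (24-month interval) instead of 5%. A test that includes the benchmark's sampling error has about 71% or 80% power. A smaller SD of change would raise both the planned test's error and the corrected power. Differences in region or population, and any between-study variation not already reflected in the intervals, would come on top, and the documents give no figure for them.

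**What to change.** In section 8.0:
- For the comparison with untreated patients, report the difference from the benchmark with a confidence interval and test based on √(s²/n + SE_hist²) and Satterthwaite df.
- Name in advance, before outcome data are seen, whether the 12-month (SE_hist 0.033) or 24-month interval (0.020) is used, and align sections 2.0 and 2.1 with that choice. Confirm from the meta-analysis that the brackets are 95% intervals.
- State that 86% power applies to a benchmark treated as known, and give about 71% (or 80%) when its sampling error is included.
- Keep the one-sample t-test as a labelled analysis against the constant −0.16.
- Note that the added term covers only sampling error of the pooled mean, not differences in region or population.

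The cost is wording and a less favourable power figure; no extra patients are needed. For information, restoring 86% for the corrected test with the 12-month interval would take about 40 completers: √(0.2²/40 + 0.0332²) = 0.0458, and 0.14/0.0458 − 1.96 = 1.10, or 86% by normal approximation. At 26.5% attrition that is 40/0.735, about 55 enrolled. The fix does not ask for this.
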